2.3.1. Risk Assessment

Potential Risk of Clinical Significance	Summary of Data/Rationale for Risk	Mitigation Strategy
Study Intervention: IW-3300		
Potential for diarrhea and secondary dehydration	These are class effects of GC-C agonism or effects observed in nonclinical safety pharmacology and toxicology studies of IW-3300.	Intrarectal administration will likely decrease the risk of diarrhea and subsequent dehydration. The study design includes dose escalation to closely monitor subject safety and tolerability at each dose level before dosing with a higher dose; a Dose Escalation Committee will conduct blinded reviews of all the safety parameters of the dosing cohort through Discharge (Day 2) in order to make decisions regarding escalation to the next dose. Orthostatic vital sign measurements will be taken to evaluate the potential for volume depletion. The daily BM frequency and stool consistency will be monitored in real time to evaluate changes in bowel habits and the potential risk of diarrhea. Stopping rules will also be in place to evaluate continued dosing (Section 7.1.1); dosing within a cohort may be temporarily suspended in the event of a diarrhea or dehydration serious adverse event (SAE); ≥ 1 subject with Grade 3 diarrhea (increase from baseline of >7 stools per day and/or watery stools [BSFS score of 7] resulting in a limiting of self-care activities) or dehydration (hospitalization indicated); or ≥ 2 subjects with Grade 2 diarrhea (increase from baseline of 4 to 6 stools per day and/or watery stools [BSFS score of 7] resulting in a limiting of instrumental activities) or dehydration (intravenous fluids indicated).

Potential Risk of Clinical Significance	Summary of Data/Rationale for Risk	Mitigation Strategy

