Unknown AEs, laboratory abnormalities, or other safety findings with a novel study drug	This is a first-in-human study with IW-3300 and, as such, there are no clinical data available.	The first cohort will feature sentinel dosing, whereby the first 2 subjects in Cohort 1 will be randomized in a 1:1 ratio to IW-3300 or placebo and dosed at least 4 hours before the remaining subjects in the cohort. Following from there, the study design includes dose escalation to closely monitor subject safety at each dose level before dosing with a higher dose; a Dose Escalation Committee will conduct blinded reviews of all the safety parameters of the dosing cohort through Discharge (Day 2) in order to make decisions regarding escalation to the next dose. Stopping rules are also in place to evaluate continued dosing within a cohort (Section 7.1.1); dosing within a cohort may be temporarily suspended in the event of an SAE considered related to study drug; ≥1 subject with a Grade 3 (severe or medically significant) or higher AE considered related to study drug; or ≥2 subjects with Grade 2 (moderate) or higher AEs considered related to study drug.
Study drug will be administered rectally.	Rectally administered medications may potentially be associated with AEs such as local trauma/discomfort, irritation, or bleeding.	The study excludes subjects for whom rectal administration would be anticipated to be a safety concern. The low-volume enema used in this study is expected to be a lower risk than higher volume enemas. Nonclinical toxicology studies of IW-3300 have shown no signs of local trauma following intrarectal administration.
Study Procedures		
Venipuncture will be performed during the study.	There is the risk of bleeding, bruising, hematoma formation, and infection at the venipuncture site.	Only appropriately qualified personnel will perform the blood draw. Subjects will be monitored for these risks and managed appropriately.

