4.2. Scientific Rationale for Study Design

A randomized, double-blind, placebo-controlled study design was chosen to investigate the safety, PK, and PD of IW-3300, and to determine the tolerability of a range of doses of IW-3300 administered rectally as a low-volume enema. Subjects will be randomized within each cohort to ensure that the treatment groups are comparable and to minimize the potential for selection bias. The study will be double-blind to ensure that the subjects and CRU staff are unaware of the treatment assignment and to minimize the potential for bias in study assessments or AE reporting. Placebo was chosen as the control so that the rate of spontaneously occurring AEs can be determined and to reduce the potential for bias in the reporting of AEs.

Subjects will complete the BM portion of the BBMD during the last 7 days of the Screening Period to establish a baseline without study drug. Subjects will be confined to the CRU for the duration of the Clinic Period, from Check-in (Day -1) through 1 day of dosing until Discharge (Day 2), which will occur after completion of the assessments (at least 24 hours after administration of study drug) and at the investigator's discretion. CRU staff will contact subjects for the Follow-up Phone Call 12 (+3) days after Discharge for safety follow-up; at the discretion of the investigator, subjects may be requested to return to the CRU for their follow-up contact.

Because this is the first-in-human study with IW-3300, Cohort 1 will feature sentinel dosing whereby the first 2 subjects will be randomized in a 1:1 ratio to receive IW-3300 or placebo, and

[figure not shown]
they will be dosed at least 4 hours before the remaining subjects in the cohort. Subsequently, the cohorts will be enrolled sequentially, following a safety review of prior dosed cohorts. In addition, stopping criteria have been established to ensure that dosing at the same or higher dose levels (a lower dose could be used) will stop should a safety signal be detected.

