6.6. Dose Modification

The decision to proceed to the next dose level of IW-3300 (either an increase or a decrease) will be made by the Dose Escalation Committee, based on blinded safety and tolerability data obtained through Discharge on Day 2 in all subjects at the prior dose level.

Dosing at a given dose level may be temporarily suspended for any of the reasons listed in Section [7.1.1](#).

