7.1.1. Study Suspension or Termination

Dosing at a given dose level may be temporarily suspended if any of the following occur within a cohort:

- ≥ 1 subject with an SAE considered related to study drug
- ≥ 1 subject with a Common Terminology Criteria for Adverse Events (CTCAE) Grade 3 or higher AE considered related to study drug (CTCAE v5.0 will be used; grading criteria are summarized in Appendix 3/Section [10.3.3](#))
- ≥ 2 subjects with CTCAE Grade 2 or higher AEs considered related to study drug

The Dose Escalation Committee should consider the benefit-risk ratio in their determination to suspend dosing temporarily or permanently. If the benefit-risk is considered unacceptable and the effect is considered related to active study drug by the Dose Escalation Committee, dosing at a given dose level will be stopped, and no additional cohorts will be dosed at the same or higher dose level (a lower dose could still be studied).

The sponsor may permanently terminate the study, or a component of the study, at any time. Reasons for termination may include, but are not limited to:

- Death, SAE, or other safety finding considered to be related to IW-3300 that may preclude further dosing.

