8.3.1. Time Period and Frequency for Collecting AE and SAE Information

All AEs and SAEs will be collected from the signing of the ICF until completion of study participation (ie, early termination or Follow-up Phone Call) at the timepoints specified in the SoA ([Table 1](#)).

Any medical condition that is present at the time that a randomized subject is screened and does not deteriorate (worsen in severity and/or frequency) should be recorded as Medical History and not as an AE. However, if the subject's condition deteriorates at any time during the study, it will be recorded as an AE. AEs characterized as intermittent require documentation of onset and duration of each episode. Pretreatment AEs will be collected and captured in the subject's source documentation from the time the subject signs the ICF until the subject receives study drug. Pretreatment AEs in randomized subjects will additionally be entered on the AE page of the subject's eCRF. Laboratory abnormalities, changes in vital signs, and physical examination findings should be considered AEs and reported on the AE page of the subject's eCRF only if the investigator considers them clinically significant and/or they necessitate intervention.

All SAEs will be recorded and reported to the sponsor or designee immediately and under no circumstance should this exceed 24 hours, as indicated in Appendix 3/Section [10.3](#). The investigator will submit any updated SAE data to the sponsor within 24 hours of it being available.

Investigators are not obligated to actively seek AEs or SAEs after the conclusion of study participation. However, if the investigator learns of any SAE, including a death, at any time after a subject has been discharged from the study, and he/she considers the event to be reasonably related to the study intervention or study participation, the investigator must promptly notify the sponsor.

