4.2. Discussion of Study Design, Including Choice of Control Group

A randomized, double-blind, placebo-controlled study design was chosen to investigate the safety, PK, and PD of IW-3300, and to determine the tolerability of a range of doses of IW-3300 administered rectally as a low-volume enema. Subjects will be randomized within each cohort to ensure that the treatment groups are comparable and to minimize the potential for selection bias. The study will be double-blind to ensure that the subjects and CRU staff are unaware of the treatment assignment and to minimize the potential for bias in study assessments or AE reporting. Placebo was chosen as the control so that the rate of spontaneously occurring AEs can be determined and to reduce the potential for bias in the reporting of AEs.

Subjects will complete the BM portion of the BBMD during the last 7 days of the Screening Period to establish a baseline without study drug. Subjects will be confined to the CRU for the duration of the Clinic Period, from Check-in (Day -1) through 1 day of dosing until Discharge (Day 2), which will occur after completion of the assessments (at least 24 hours after administration of study drug) and at the investigator's discretion. CRU staff will contact subjects for the Follow-up Phone Call 12 (+3) days after Discharge for safety follow-up; at the discretion of the investigator, subjects may be requested to return to the CRU for their follow-up contact.

Because this is the first-in-human study with IW-3300, Cohort 1 will feature sentinel dosing whereby the first 2 subjects will be randomized in a 1:1 ratio to receive IW-3300 or placebo, and they will be dosed at least 4 hours before the remaining subjects in the cohort. Subsequently, the cohorts will be enrolled sequentially, following a safety review of prior dosed cohorts. In addition, stopping criteria have been established to ensure that dosing at the same or higher dose levels (a lower dose could be used) will stop should a safety signal be detected.

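### A met stopping trigger does not oblige anyone to hold the next subject in the same cohort while the Dose Escalation Committee decides

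*Protocol*

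**What the plan says.** Protocol 7.1.1 introduces its three triggers with "Dosing at a given dose level may be temporarily suspended if any of the following occur within a cohort". It then passes the matter to the committee: "The Dose Escalation Committee should consider the benefit-risk ratio in their determination to suspend dosing temporarily or permanently". If the committee finds benefit-risk unacceptable and considers the effect related to active drug, dosing at that level must stop and no further cohort may receive that dose or a higher one.

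The permissive wording recurs. Under Protocol 6.6, dosing "may be temporarily suspended for any of the reasons listed in Section" 7.1.1. In Protocol 2.3.1, the row on unknown AEs says "Stopping rules are also in place to evaluate continued dosing within a cohort (Section 7.1.1); dosing within a cohort may be temporarily suspended". The row on diarrhea and dehydration says "dosing within a cohort may be temporarily suspended in the event of a diarrhea or dehydration serious adverse event (SAE", and goes on to Grade 3 and Grade 2 conditions. None of that row's triggers requires the event to be related to study drug, whereas all three in 7.1.1 do.

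Protocol 4.2 and SAP 4.2 describe the purpose of the criteria in firmer terms. In the SAP, "stopping criteria have been established to ensure that dosing at the same or higher dose levels (a lower dose could be used) will stop"; the protocol sentence ends "will stop should a safety signal be detected".

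Two holds are mandatory. Cohorts 2 to 5 start only after review of the prior cohort (Protocol 1.1.8 and 6). In Cohort 1 the last six subjects are dosed only if no safety signal is noted in the two sentinels over at least 4 hours (Protocol 4.1).

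**The concern.** A stopping rule has to say what happens to the next subject when a trigger is met. Here the triggers are precise and the consequence is optional. The decision belongs to a committee of sponsor and CRO representatives, and the protocol gives no time by which it must meet or decide. The site could therefore dose the remaining subjects of a cohort after a met trigger without a protocol deviation.

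The reporting clock does not close the interval. Protocol 8.3.1 requires SAEs to be reported "immediately and under no circumstance should this exceed 24 hours", but that limit covers SAEs only. Protocol 10.3.3.2 separates seriousness from severity, so a related Grade 3 AE, or two related Grade 2 AEs, can meet a trigger without being serious.

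At stake is whether more healthy volunteers in a first-in-human study receive a dose level that has just met a trigger, before anyone has reviewed the event.

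**Working it through.** The plan gives no figure to reproduce: there is no hypothesis test and no sample size calculation (Protocol 9.1, 9.2). The check is a comparison of the relevant text, followed by a count that rests on assumptions.

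**Step 1. What each provision does between a met trigger and the committee's decision**

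| Provision | Effect | Holds the next subject in the cohort? |
|---|---|---|
| 7.1.1 triggers; 6.6; 2.3.1 (two rows) | Suspension permitted | Not required |
| 7.1.1 committee stop | Mandatory, after an adverse committee finding | Only after the decision |
| Review before each of Cohorts 2 to 5 | Mandatory | No; protects the next cohort |
| Cohort 1 sentinel step | Mandatory, at least 4 hours | Yes, for the six who follow; not among those six once dosing starts |
| Section 8, immediate discussion with the sponsor | Addresses whether the affected subject continues study drug | No |
| 8.3.1, 24-hour limit | Reporting, SAEs only | No |
| 10.1.5 sponsor monitoring; 2.3.1 real-time stool monitoring | Detection | No |
| 7.1.1 sponsor termination; 7.2 withdrawal by the investigator | Discretionary | Not required |

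Only the sentinel step holds subjects within a cohort, and it ends before the rest of Cohort 1 is dosed.

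**Step 2. Who is in scope**

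- Cohorts 2 to 5: the later subjects of each cohort of 8 (6 active, 2 placebo).
- Cohort 1 after the sentinels: 8 − 2 = 6 subjects, of whom 6 − 1 = 5 are active.

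**Step 3. How many subjects a mandatory hold would cover**

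Two inputs are needed and neither is stated: the interval *d* between subjects and the time *r* from dosing to recognition of the trigger. Assume even spacing, and that a subject due exactly at recognition is held. In a cohort of 8, the number still undosed at recognition is:

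- one-subject trigger in the first subject: 8 − min(8, ceil(*r*/*d*))
- two-subject trigger in the first two, with *r* counted from the second dose: 8 − min(8, ceil(*r*/*d*) + 1)

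| *d* | *r* = 2 h, one-subject | *r* = 2 h, two-subject | *r* = 4 h, one-subject | *r* = 4 h, two-subject |
|---|---|---|---|---|
| 15 min | 0 | 0 | 0 | 0 |
| 30 min | 4 | 3 | 0 | 0 |
| 60 min | 6 | 5 | 4 | 3 |
| 120 min | 7 | 6 | 6 | 5 |
| 24 h | 7 | 6 | 7 | 6 |

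Example: *r* = 2 h and *d* = 60 min give ceil(120/60) = 2 dosed, so 8 − 2 = 6 undosed, or 8 − 3 = 5 for the two-subject trigger.

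For the six post-sentinel subjects of Cohort 1, with the events among those six, the upper ends are 6 − 1 = 5 and 6 − 2 = 4. The lower end is again 0.

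These are upper counts in one respect: they place the trigger in the first subject or the first two. They count subjects whom a hold would cover, not subjects who would be harmed.

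**The case against.** The strongest reply is that discretion here is a choice and that other protections exist. The sponsor may terminate all or part of the study at any time. The investigator may withdraw a subject for safety, including one randomized but not yet dosed. The committee may act before discharge, since the Day 2 data rule in 6.6 governs the next dose level. The top dose is about one tenth of the human equivalent of the lowest NOAEL (Protocol 4.3), and nonclinical systemic bioavailability is at most 0.2% (Protocol 2.2). All of this is correct. It makes a trigger less likely and a voluntary pause more likely, but it does not require a pause.

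A second reply is that a hold may protect nobody. Subjects are assessed and randomized on the morning of Day 1 (Protocol 4.1.1.2) and product is compounded that day (6.2), so close spacing is plausible. That stands, and it is why the range starts at 0.

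A third is that, under the blind, placebo or the enema itself can meet a trigger. That also stands, as a cost of the change.

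Three stronger readings might be inferred, and the documents do not support them.

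- *That 4.2 contradicts 7.1.1.* Its terms (same or higher dose levels, with a lower dose still possible) closely match the committee stop in 7.1.1, and it does not define a safety signal as a met trigger. It most naturally summarises that stop. Its wording is firmer than the trigger sentence, but the two do not conflict.
- *That everyone in Cohorts 2 to 5 is exposed to the gap.* The total of 4 × 8 = 32 subjects (4 × 6 = 24 active) is maximum enrolment in those cohorts, not the number undosed after a trigger. It also leaves out the six in Cohort 1.
- *That the 2.3.1 diarrhea and dehydration triggers should gain a relatedness condition to match 7.1.1.* That would narrow a safety trigger for the class effect the protocol itself names.

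**Conclusion.** The point holds as a gap in the within-cohort rule. Once a trigger is met, suspension is optional, and no provision holds the next subject in the same cohort until the committee decides. It applies within Cohorts 2 to 5 and among the six post-sentinel subjects of Cohort 1. It does not extend to escalation between cohorts, and it does not mean that the protocol lacks a mandatory stop.

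The finding about the wording needs no assumption. Its practical size does: in a cohort of 8 a hold would cover 0 to 7 subjects for a one-subject trigger and 0 to 6 for a two-subject trigger, depending on the unstated interval and recognition time. Because the benefit may be nil, the case rests on the low cost of the change and on the population, healthy volunteers receiving a drug for the first time in humans. It is a recommended correction, and the committee's judgment on whether to resume or stop stays as written.

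**What to change.** 1. **Protocol 7.1.1.** Replace the sentence that introduces the triggers with: *Dosing at a given dose level will be suspended as soon as the investigator is aware that any of the following has occurred within a cohort; no further subject will be dosed at that or a higher dose level until the Dose Escalation Committee has reviewed the event and documented its decision.*
2. **Protocol 6.6 and both rows of 2.3.1.** Change the permissive phrase to: *will be suspended pending Dose Escalation Committee review.*
3. **Diarrhea and dehydration triggers.** Leave them without a relatedness condition. If the sections are harmonised, carry the 2.3.1 triggers into 7.1.1 as written.

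No sentinel step or fixed dosing interval is requested for later cohorts, and no deadline for the committee is needed once dosing waits for its decision.

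The cost is wording in three sections. In conduct, a trigger met mid-cohort brings a short pause and an ad hoc blinded review, even when the event comes from placebo (2 of 8 subjects) or from the enema. Some subjects may need rescheduling, and doses compounded that day may be lost. No subjects, visits or assessments are added to the plan.

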7.2. Subject Discontinuation/Withdrawal from the Study

- A subject may withdraw from the study at any time at his/her own request or may be withdrawn at any time at the discretion of the investigator for safety, behavioral, compliance, or administrative reasons. This is expected to be uncommon.
- At the time of discontinuation from the study, if possible, an early discontinuation visit should be conducted, as shown in the SoA ([Table 1](#)). See SoA for data to be collected at the time of study discontinuation and follow-up and for any further evaluations that need to be completed.
- The subject will be permanently discontinued both from the study intervention and from the study at that time.

- If the subject withdraws consent for disclosure of future information, the sponsor may retain and continue to use any data collected before such a withdrawal of consent.
- If a subject withdraws from the study, he/she may request destruction of any samples taken and not tested, and the investigator must document this in the site study records.

7.3. Lost to Follow-up

A subject will be considered lost to follow-up if he or she repeatedly fails to return for scheduled visits and is unable to be contacted by the study site.

The following actions must be taken if a subject fails to return to the clinic for a required study visit:

- The site must attempt to contact the subject, reschedule the missed visit as soon as possible, counsel the subject on the importance of maintaining the assigned visit schedule, and ascertain whether or not the subject wishes to and/or should continue in the study.
- Before a subject is deemed lost to follow up, the investigator or designee must make every effort to regain contact with the subject (where possible, 3 telephone calls and, if necessary, a certified letter to the subject's last known mailing address or local equivalent methods). These contact attempts should be documented in the subject's medical record.
- Should the subject continue to be unreachable, he/she will be considered to have withdrawn from the study and reason for discontinuation will be "lost to follow-up."

Discontinuation of the site or of the study as a whole are handled as part of Appendix 1/Section 10.1.

8. STUDY ASSESSMENTS AND PROCEDURES

- Study procedures and their timing are summarized in the SoA ([Table 1](#)). Protocol waivers or exemptions are not allowed.
- Immediate safety concerns should be discussed with the sponsor immediately upon occurrence or awareness to determine if the subject should continue or discontinue study drug.
- Adherence to the study design requirements, including those specified in the SoA, is essential and required for study conduct.
- All screening evaluations must be completed and reviewed to confirm that potential subjects meet all eligibility criteria. The investigator will maintain a screening log to record details of all subjects screened and to confirm eligibility or record reasons for screening failure, as applicable.

